6.3 MEASURES TO MINIMIZE BIAS: RANDOMIZATION AND BLINDING

Participants will be randomized to treatment arm (MC, Control)* stratified by sex and MoCA score [25/26]⁶⁵. The study statistician created a randomization process that is implemented through REDCap by an independent person ([name]). Immediately after a participant completes Pre assessment, the tester informs [name], via email, of their study ID, sex, and MoCA score (stratification variables). Within 2 days of being informed, [name] will use the REDCap randomizer to assign treatment group and will inform the corresponding therapists, via email, that a participant has been assigned to their group. Only [name] and the statistician can view the randomizer and its results. To maintain PI blinding during therapist supervision, the participants or treatment sessions under discussion will not be identified by study ID.

Personnel collecting Pre, Post and Follow-up data, which includes the study coordinator, will remain blind to treatment arm throughout the entirety of the study. They will not know which therapists are administering which intervention. Inadvertent unblinding of testers will be documented (yes/no, notes). Most of the outcomes, including the primary efficacy outcome (BGSI, Aim 3), are collected via computer, so inadvertent unblinding should not bias the data.

Personnel responsible for rating the audio files for fidelity (Aim 2) will be blind to study purpose. Due to the nature of their work, they will likely come to understand that there are two general intervention approaches being delivered and which therapists are delivering which approach; however, having no knowledge of the study aims and hypotheses and clear criteria for rating should reduce any associated biases in their ratings.

Participants will be aware that they have been randomly assigned to one of two interventions, but they will be given no information on what the other intervention entails, nor will they be informed which is the hypothesized “active” (MC) or Control intervention. In the Follow-up assessment, participants will be asked if they think they received the active or control intervention (yes/no/I don’t know with an option to provide an open-ended response describing why).

*Randomization ratios over the course of the study due to therapist availability:

- November 2019-December 2020 = 2:1, MC:Control
- January 2021- ~2021 = 1:2, MC:Control
- ~July 2021- = 1:1, MC:Control

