9.2 SAMPLE SIZE DETERMINATION

We will enroll 30 participants per group ($N = 60$). Although not required for an R21 proposal, we provide power analyses for our feasibility and fidelity hypotheses (Aims 1 & 2) assuming 15% attrition (see Table). We also estimate power for our (exploratory) pre-post comparisons of treatment effect (Aim 3). Based on our preliminary data (Goal Attainment $\Delta M = 2.4$, $SD = 0.97$), with $n = 30$ per group we will be able to detect mean differences in change of 0.85 in Attainment (2-tailed, $\alpha = 0.05$, 90% power). However, we want to reiterate that our reason for measuring treatment effect in this study is not to demonstrate efficacy but to obtain effect size estimates to power an efficacy trial. Our proposed sample size will provide enough information to achieve our aims and is feasible to accomplish in the timeframe of an R21.

Confidence bounds around target thresholds assuming 15% attrition (for Aim 2) and 95% confidence level.		
Aim	Outcome (with preliminary data source reference)	Target (Lower, upper)
1	Recruitment and retention	85% (73 – 93)
2a	Adherence (n=153 observations) ⁶¹	80% (78 - 82)

2a	Proficiency (n=153 observations) ⁶¹	3 (2.9 – 3.1)
2b	Acceptance: CSQ ⁵³	24 (23.8 – 24.2)
2b	Receipt: PRPS ⁷⁸	4 (3.8 – 4.2)
2b	Enactment: Homework completion ⁵³	80% (75 – 85)

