For the Aim 2 outcomes, we will calculate mean scores $\pm 95\%$ confidence bounds (CBs) and compare them to our stated thresholds. To assess treatment differentiation, we will compare Proficiency scores for the MC and Control sessions using *t*-tests. We can also categorize participants using cutoffs (e.g., homework: <50% = Poor, 50-79% = Fair, $\geq 80\%$ = Good) for descriptive purposes and compare the MC and Control groups’ scores on outcomes using appropriate non-parametric tests.

Aim 3: Obtain preliminary estimates of the MC approach's effect on patient-reported functional cognition.

- H3 (exploratory): MC participants will report greater improvement in functional cognition than Control participants immediately and 3 months after treatment.

We will compare treatment effects (Goal Attainment) using mixed model repeated measures ANOVA (2: group X 3: time point). We chose this model because we want to use statistical contrasts to compare pre-post and pre-follow up changes across group. We will evaluate the pattern of correlations within subjects and test various correlation structures as appropriate using Akaike's information criteria and the Schwarz Bayesian criteria. However, our purpose is not to demonstrate efficacy, but rather to obtain effect size data to inform sample size calculations for a definitive RCT. To this end, we will generate mean change between the time points with 95% CIs. We will compare these data to the suggested minimally clinically important difference (≥ 2 points improvement)⁸⁹ to help determine the appropriate sample size to test the hypothesis that, in addition to being superior to the Control treatment, MC produces a clinically significant effect⁹⁰. We will also create a sample size table for various effect size values due to uncertainty of pilot estimates⁹¹.

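### Therapists appear to be nested within arm, but the Aim 3 intervals and the planned sample-size table make no allowance for therapist clustering; if therapist correlation is positive, both will be too optimistic.

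*Combined protocol and SAP*

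**What the plan says.** **Delivery.** Section 6.3 says that after each assignment the independent person "will inform the corresponding therapists, via email, that a participant has been assigned to their group". The same section keeps testers unaware of which therapist gives which treatment, and expects the fidelity raters to work this out. It also lists "Randomization ratios over the course of the study due to therapist availability", moving from 2:1 to 1:2 to 1:1. Section 6.2.1 sets separate training for MC and Control. Treatment is individual (section 6.1.2), so any clustering is by therapist and not by treatment group session.

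**Analysis.** Section 9.4 says of Aim 3: "We will compare treatment effects (Goal Attainment) using mixed model repeated measures ANOVA", with two groups and three time points. Correlation structures are to be chosen for repeated measurements within a participant. Mean changes will carry 95% intervals.

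**Planning.** Section 9.2 says "We will enroll 30 participants per group" and, from an SD of 0.97, "we will be able to detect mean differences in change of 0.85 in Attainment" ("2-tailed, $\alpha = 0.05$, 90% power"). For the definitive trial, section 9.4 will "create a sample size table for various effect size values due to uncertainty of pilot estimates". No therapist term, ICC, design effect or cluster-robust variance appears anywhere, and the number of therapists is not given.

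**The concern.** When therapists work in one arm only, differences between therapists become part of the difference between arms. An analysis that treats participants as independent leaves that variance out of the standard error of the contrast.

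The protocol gives reasons to expect some therapist effect. Under section 8.1 the therapist leads the goal interview, helps to set the goals, and holds the second session, where the Pre attainment ratings are made. All of this follows randomization. Section 2.2 links fidelity to better outcomes, and section 9.4 summarises adherence and proficiency for each therapist. The plan thus looks at therapist variation in delivery but not in outcome.

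Aim 3's stated product is effect-size information for a definitive RCT. An interval that is too narrow, followed by a table without a design effect, would carry the same omission into the size of that trial.

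**Working it through.** **Inputs from the documents (section 9.2):** n = 30 per arm; SD of change 0.97; two-sided alpha 0.05; power 90%; stated detectable difference 0.85.

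**Assumptions, not in the documents:** k = 2 or 3 therapists per arm with equal caseloads; ICC of the change in Goal Attainment 0.01, 0.05 or 0.10.

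**Step 1. Reproduce the plan's figure.** For two independent means, n = 2 × (1.960 + 1.282)² × 0.97² / 0.85² = 27.4, so 28 per arm, or 29 with the noncentral t. The plan has 30. In reverse, n = 30 gives (1.960 + 1.282) × 0.97 × sqrt(2/30) = 0.81, or 0.83 with the t. The stated 0.85 is therefore an ordinary independent-samples figure, slightly conservative, with no clustering allowance. It has no attrition allowance either: it is stated at 30 per group, and the table in section 9.2 is headed "Confidence bounds around target thresholds assuming 15% attrition (for Aim 2) and 95% confidence level".

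**Step 2. Add clustering.** Design effect DE = 1 + (m − 1) × ICC, with m = 30/k. The SE and the interval half-width are multiplied by sqrt(DE), and the detectable difference becomes 0.85 × sqrt(DE).

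| Therapists per arm | m | ICC | DE | SE multiplier | Detectable difference |
|---|---|---|---|---|---|
| 2 | 15 | 0.01 | 1.14 | 1.07 | 0.91 |
| 2 | 15 | 0.05 | 1.70 | 1.30 | 1.11 |
| 2 | 15 | 0.10 | 2.40 | 1.55 | 1.32 |
| 3 | 10 | 0.01 | 1.09 | 1.04 | 0.89 |
| 3 | 10 | 0.05 | 1.45 | 1.20 | 1.02 |
| 3 | 10 | 0.10 | 1.90 | 1.38 | 1.17 |

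At ICC = 0, DE = 1 and nothing changes.

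**Step 3. What the table leaves out.**
- *Unequal caseloads.* The relevant m is sum(m_i²)/sum(m_i), which equals the mean caseload times (1 + CV²), where CV is the coefficient of variation of the caseloads. The changing ratios make unequal caseloads likely, so the mean would understate DE.
- *Few therapists.* Estimating therapist variance from the pilot would leave 2(k − 1) degrees of freedom: 2 with two per arm (t = 4.30) and 4 with three (t = 2.78). A fitted random therapist effect is therefore not a workable remedy, and an assumed ICC range is.
- *One therapist per arm.* Therapist and treatment cannot then be separated by any model.

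**Step 4. Illustration for the next trial.** Take a difference of 0.5 (assumed), SD 0.97 and 90% power. Independence gives 2 × (1.960 + 1.282)² × 0.97² / 0.5² = 79.1, so 80 per arm. With an assumed 10 participants per nested therapist, multiplying by 1.09, 1.45 and 1.90 gives 88, 116 and 152 per arm.

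**The case against.** The strongest reply is that Aim 3 is exploratory. Sections 9.2 and 9.4 both say that its purpose is not to show efficacy, and section 9.4 already acknowledges that pilot estimates are uncertain. No efficacy conclusion depends on the between-arm interval. This stands, and it limits the weight of the point. It does not remove the point, because sizing the next trial is what Aim 3 is for.

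Training, tape review and per-therapist fidelity benchmarks may reduce therapist differences. They do not adjust the intervals.

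A table spanning effect sizes may also happen to contain the larger sample sizes: a DE of 1.70 acts like a 23% smaller effect (1 − 1/sqrt(1.70)), and 2.40 like a 35% smaller one. That is true, but a reader of the table could not tell which row allows for clustering.

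Three stronger readings are tempting, and the documents do not support them:
- That the intervals and table are bound to be too optimistic. This requires ICC > 0, and no ICC is given.
- That the table assumes independence. It does not yet exist, and its variance assumptions are not described. A design effect is unmentioned, not excluded, and whether therapists would be nested in the definitive trial is not stated.
- That one arm per therapist is an established fact. Section 6.3 points firmly that way, but no sentence says it.

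**Conclusion.** The point holds conditionally. Therapists are very probably nested in arm, the stated Aim 3 model ignores any correlation between participants who share one, and the planning table is described as varying by effect size only. If the therapist ICC is positive, the between-arm 95% intervals will be too narrow, and a table without a design effect will undersize a definitive trial with nested therapists.

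On the assumptions above, the understatement runs from slight (4% to 7% in SE at ICC 0.01) to substantial (38% to 55% at ICC 0.10). These figures show a range. They are not estimates for this trial, because the ICC, the therapist numbers and the caseloads are all assumed.

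A reader might also infer that the Aim 3 failure rule in section 3 is undermined, since it uses a lower 95% bound. That rule refers to average change and does not say that it applies to the MC-minus-Control contrast, so the point is not rested on it. The main consequence is for the design of the next trial. The change is worth making because it is cheap and serves Aim 3's stated purpose.

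**What to change.** Keep the primary model and add to section 9.4:

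1. Report the number of therapists and the caseloads in each arm, and the mean change in Goal Attainment by therapist.
2. For each between-arm contrast, give a sensitivity 95% interval with the SE multiplied by sqrt(1 + (m − 1) × ICC) for ICC 0.01, 0.05 and 0.10, where m = sum(m_i²)/sum(m_i) so that unequal caseloads count. Describe the primary interval as conditional on these therapists, and say that with one therapist per arm the therapist and treatment effects cannot be separated.
3. Add therapist ICC and participants per therapist as dimensions of the sample-size table.

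State in section 6.3 whether each therapist delivers one arm only.

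The cost is a few lines of text and a small amount of analysis. The downside is a wider sensitivity interval and larger sample sizes in the table.

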10 SUPPORTING DOCUMENTATION AND OPERATIONAL CONSIDERATIONS

10.1 REGULATORY, ETHICAL, AND STUDY OVERSIGHT CONSIDERATIONS

10.1.1 INFORMED CONSENT PROCESS

10.1.1.1 CONSENT/ASSENT AND OTHER INFORMATIONAL DOCUMENTS PROVIDED TO PARTICIPANTS

See Informed Consent document

10.1.1.2 CONSENT PROCEDURES AND DOCUMENTATION

See the Data & Safety Monitoring Plan

10.1.2 STUDY DISCONTINUATION AND CLOSURE

This study may be temporarily suspended or prematurely terminated if there is sufficient reasonable cause. If the study is prematurely terminated or suspended, the Principal Investigator (PI) will promptly inform study participants, the Institutional Review Board (IRB), and sponsor/funding agency and will provide the reason(s) for the termination or suspension. Study participants will be contacted, as applicable, and be informed of changes to study visit schedule.

Circumstances that may warrant termination or suspension of the study include, but are not limited to determination of unexpected, significant, or unacceptable risk to participants, significant protocol violations, or determination of futility.

The study may resume once concerns about safety, protocol compliance, and data quality are addressed, and satisfy the funding agency, sponsor, IRB, Food and Drug Administration (FDA), or other relevant regulatory or oversight bodies (OHRP, DSMB).]

10.1.3 CONFIDENTIALITY AND PRIVACY

Participant confidentiality and privacy is strictly held in trust by the participating investigators, their staff, the safety monitor, and funding agency and will be maintained in accordance with applicable state and federal laws. This confidentiality is extended to the data being collected as part of this study. Data that could be used to identify a specific study participant will be held in strict confidence within the research team. No personally-identifiable information from the study will be released to any unauthorized third party without prior written approval of the IRB.

All research activities will be conducted in as private a setting as possible. The study participants' contact information will be securely stored for internal use during the study. At the end of the study, all records will continue to be kept in a secure location for as long a period as dictated by the reviewing IRB, institutional policies, or sponsor/funding agency requirements.

Participant data will be coded numerically to protect individual identity. No identifiers will be used in presentations or publications. All data will be stored in locked cabinets or on computers within a private security network protected by a Cisco PIX firewall with remote access only permitted through VPN connections, as per HIPAA guidelines. All key personnel involved in the design or conduct of research involving the human subjects will receive the required education on the protection of human research participants.

Participants are asked the following question at Follow-up assessment to monitor for perceived confidentiality breach:

“Do you feel that the study team has protected your privacy over the course of the study?
Yes/No”

See also the Data Sharing Plan

10.1.4 SAFETY OVERSIGHT

See the Data & Safety Monitoring Plan

10.1.5 DATA HANDLING AND RECORD KEEPING

10.1.5.1 DATA COLLECTION AND MANAGEMENT RESPONSIBILITIES

Appropriate records will be maintained for this trial, in compliance with ICH GCP and regulatory and institutional requirements for the protection of confidentiality of participants. As part of participating in a NIH-sponsored study, the site will permit authorized representatives of the NIH, sponsor, and regulatory agencies to examine (and when permitted by applicable law, to copy) research records for the purposes of quality assurance reviews, audits, and evaluation of the study safety, progress, and data validity.

Both paper and electronic data capture will be used for this study, and all quantitative data will ultimately be entered into the study's REDCap database. Data not collected directly by REDCap (e.g., those administered via REDCap Survey Mode) or imported from another electronic source directly into REDCap (e.g., NIH Toolbox Cognitive Battery and NeuroQOL data) will be entered by trained research personnel using a double scoring/entry and automated discrepancy flagging protocol to minimize errors.

Paper sources of data include some of the Pre and Post assessments, questionnaires for participants who opt for hard copy completion, all of the record forms and worksheets completed during the treatment sessions, and the treatment fidelity assessments. Electronic sources of data include electronic medical records (e.g., PD-related clinical characteristics), NIH Toolbox Cognitive Battery, NeuroQOL questionnaires, REDCap Survey Mode (web-based questionnaire delivery), and audio recordings of treatment sessions.

Data collection will be the responsibility of the testers and therapists under supervision of the study coordinator and PI. The coordinator and PI will be responsible for ensuring the accuracy, completeness, legibility, and timeliness of the data reported as well as storage and management of source data. Hardcopies of the study visit worksheets will be maintained for future reference but will also be scanned and stored in a secure, web-based location for access by research personnel.

10.1.5.2 STUDY RECORDS RETENTION

Data collected under this protocol will be kept for a minimum of 7 years after the study is complete, as per IRB policy.

10.1.6 PUBLICATION AND DATA SHARING POLICY

See Data Sharing Plan and Dissemination Plan

10.1.7 CONFLICT OF INTEREST POLICY

The independence of this study from any actual or perceived influence is critical. Therefore, any actual conflict of interest of persons who have a role in the design, conduct, analysis, publication, or any aspect of this trial will be disclosed and managed. Furthermore, persons who have a perceived conflict of interest will be required to have such conflicts managed in a way that is appropriate to their participation in the design and conduct of this trial. The university has established policies and procedures for disclosing all conflicts of interest and established mechanisms for the management of all reported dualities of interest.

10.2 PROTOCOL AMENDMENT HISTORY

*The table below is intended to capture changes of versions of the protocol, including a description of the change and rationale. A **Summary of Changes** table for the current amendment is located in the **Protocol Title Page**.*

Version	Date	Description of Change	Brief Rationale
2	May 2020	Changed randomization process and related communication among team members	To remove PI from randomization process and blind her to study group; minimize bias
2	May 2020	All participants will undergo 10 treatment sessions	To ensure treatment groups are balanced on dose of intervention
2	May 2020	Changed definition of screen failure from what was initially provided by this template	Study monitor request
2	May 2020	Added criteria used to declare failure for each aim to Objectives and Endpoints section	To enhance rigor and inform decision-making for next steps
2	May 2020	Specified target interval limits for timing of assessment and treatment sessions (see Schema)	To enhance rigor
2	May 2020	Added question to AE report form to monitor for psychological risks	A stated risk of the study, needed to capture it
2	May 2020	Added a question to the Follow-up assessment to monitor for perceived confidentiality breach	A stated risk of the study, needed to capture it
3	Nov 2020	Fixed Schedule of Activities table to indicate that inclusion/exclusion criteria are assessed in Visit 1 (via MoCA); consent form will also be modified to include this information	To fix a prior inconsistency pointed out by study monitor
4	Dec 2020	Added phone/blind MoCA to screening phone call	To reduce risk of enrolling people who do not meet cognitive criteria for entry
4	Dec 2020	Specified randomization ratio changes over course of study	To enhance transparency
5	May 2021	Added note that participants excluded post-randomization count as failures in retention endpoints	To enhance rigor and transparency

